### 14.4.3.3 Results

The simulated operating characteristics presented show that the BLRM performs well under the hypothetical profiles investigated. Indeed, the simulations performed illustrate that the model has reasonable operating characteristics and the number of patients with DLT was limited through a trial. In scenario 1, the odds of DLT are aligned with the prior information. In this scenario, the simulations show that about 49% and 23% of chance for selecting MTD at 3mg/kg and 10mg/kg dose levels, respectively. Finally, in scenario 4, with 5-fold odds inflation from test scenario 1, the chance to stop the trial due to high toxicity of all dose levels is very high (49.7%) as expected since only 0.3 mg/kg dose has the underlying P (DLT) that is below 33%. The simulations show that there is about 23% of chance for selecting MTD at 1mg/kg dose level since the assumed P(DLT) for this dose lies very close to the upper boundary of at those doses the target interval, leading to a tendency for the model estimate of the probability of overdose to identify this as a dose not satisfying the EWOC criterion.

In conclusion, the simulations performed illustrate that the model has good operating characteristics under the 4 hypothetical profiles investigated.

Amendment 1	07Jul2019	
1. Added list of abbreviations and glossary terms.2. Updated study design adding TNBC and Mesothelioma indications.3. Removed single agent groups from Phase II part.4. Updated the definition of DDS by adding specific wording for different dosing regimens.5. Added the definitions for immunogenicity analysis sets.6. Updated medical history section by adding more details on the analysis.7. Added a subsection on analysis set exclusion.8. Updated the definitions of last date of exposure for both monotherapy and combo therapy.9. Updated definitions of duration of exposure and actual cumulative dose.10. Removed the definitions of cumulative planned doses, percentage of days dosed and percentage of days at planned dose.11. Removed the language about the primary bayesian analysis of ORR for single agent LAG525.12. Added definitions of efficacy endpoints like BOR, ORR, DOR, PFS and TTR.13. Updated language on the efficacy analysis will be done for all patients. Added language about efficacy analysis for patients who switched from single agent to combination.14. Added language on safety summaries and patients who switched from single agent and combination.15. Added language on data analysis for safety and laboratory data.16. Clarified notable high or low values for vital signs.17. Updated language about PK parameters and the PK analysis.18. Added immunogenicity analysis section.19. Added details about calculation of baseline in the appendix.20. Added imputation rules in the appendix.21. Added definitions and derivation rules for irRC in the appendix.22. Removed languages on the construction of waterfall plots and cycle definition.23. Updated the references.
Amendment 2	15Jul2019	Updated language for baseline calculations for efficacy assessments.
Amendment 3	29Oct2020	Clarified PPS
Amendment 4	21Jan2021	Section 2.11.1.1 – Removed from the definition of determinant samples the exclusion for the ADA-inconclusive sample Section 2.8.2.2 - Added information regarding lab conversion units for T4 and regarding the imputed units for the normal ranges.
Amendment 5	15Mar2021	Section 2.8.2.3 – Removed Listing of all clinically relevant laboratory data with values flagged; added tables for worst post-baseline

Version	Date	Changes
		hematology and biochemistry abnormalities based on CTC grades; removed from Table 2-4 'total protein'

List of abbreviations

AE	Adverse Event
ALT	Alanine aminotransferase/glutamic pyruvic transaminase/GPT
AST	Aspartate aminotransferase/glutamic oxaloacetic transaminase/GOT
AUC	Area Under the Curve
AUCtau	Area Under the Curve for time 0 to tau
BHM	Bayesian Hierarchical Model
BLRM	Bayesian Logistic Regression Model
BOR	Best Overall Response
CR	Complete Response
CRF	Case Report/Record Form; the term CRF can be applied to either EDC or Paper
CRO	Contract Research Organization
CSR	Clinical study report
CTCAE	Common Terminology Criteria for Adverse Events
DAR	Dosage administration record
DCR	Disease Control Rate
DDP	Dose Determining Pharmacokinetic Set
DDS	Dose-Determining Safety Set
DI	Dose intensity
DLT	Dose Limiting Toxicity
DOR	Duration of Response
ECG	Electrocardiogram
EDC	Electronic Data Capture
EOS	End of Study
EOT	End of Treatment
EWOC	Escalation With Overdose Control
FAS	Full Analysis Set
i.v.	Intravenous(ly)
ICF	Informed Consent Form
█	█
IG	Immunogenicity
█	█
IL-6	Interleukin-6
irRC	immune related Response Criteria
LAG-3	Lymphocyte activation gene-3
MTD	Maximum Tolerated Dose
NSCLC	Non-Small Cell Lung Carcinoma
ORR	Overall Response Rate
█	█
PAS	Pharmacokinetic Analysis Set
PD	Pharmacodynamics
PDI	Planned dose intensity
PD-1	Programmed Death-1
PD-L1	Programmed Death-Ligand 1
PD-L2	Programmed Death-Ligand 2
PFS	Progression Free Survival
PK	Pharmacokinetics
PPS	Per Protocol Set

PR	Partial Response
PT	Preferred term
RAP	Report and Analysis Plan
RCC	Renal Cell Carcinoma
RDI	Relative dose intensity
RECIST	Response Evaluation Criteria In Solid Tumors
RP2D	Recommended phase 2 dose
SAE(s)	Serious Adverse Event(s)
SOC	System organ class
SOD	Sum of diameters
SSD	Study Specific Document
TIL(s)	Tumor Infiltrating Lymphocyte(s)
█	█
TMTB	Total measurable disease burden
TNBC	Triple Negative Breast Cancer

Glossary of terms

Assessment	A procedure used to generate data required by the study
Biologic samples	A biological specimen including, for example, blood (plasma, serum), saliva, tissue, urine, stool, etc. taken from a study subject or study patient
Cohort	A group of newly enrolled patients treated at a specific dose and regimen (i.e. treatment group) at the same time
Cycles	Number and timing or recommended repetitions of therapy are usually expressed as number of days (e.g.: q28 days)
Dose level	The dose of drug given to the patient (total daily or weekly etc.)
Enrollment	Point/time of patient entry into the study; the point at which informed consent must be obtained (i.e. prior to starting any of the procedures described in the protocol)
Investigational drug	The study treatment whose properties are being tested in the study; this definition is consistent with US CFR 21 Section 312.3 and is synonymous with "investigational new drug."
Investigational treatment	Drug whose properties are being tested in the study as well as their associated placebo and active treatment controls (when applicable). This also includes approved drugs used outside of their indication/approved dosage, or that are tested in a fixed combination. Investigational treatment generally does not include other study treatments administered as concomitant background therapy required or allowed by the protocol when used in within approved indication/dosage
Patient Number (Patient No.)	A unique identifying number assigned to each patient who enrolls in the study
Premature patient withdrawal	Point/time when the patient exits from the study prior to the planned completion of all study treatment administration and/or assessments; at this time all study treatment administration is discontinued and no further assessments are planned, unless the patient will be followed for progression and/or survival
Stage in cancer	The extent of a cancer in the body. Staging is usually based on the size of the tumor, whether lymph nodes contain cancer, and whether the cancer has spread from the original site to other parts of the body
Stop study participation	Point/time at which the patient came in for a final evaluation visit or when study treatment was discontinued whichever is later
Study treatment	Includes any drug or combination of drugs in any study arm administered to the patient as part of the required study procedures, including placebo and active drug run-ins. In specific examples, it is important to judge investigational treatment component relationship relative to a study treatment combination; study treatment in this case refers to the investigational and non-investigational treatments in combination.
Study treatment discontinuation	Point/time when a patient permanently discontinues study treatment for any reason
Treatment group	A treatment group defines the dose and regimen or the combination, and may consist of 1 or more cohorts. Cohorts are not expanded, new cohorts are enrolled.
Variable	Identifier used in the data analysis; derived directly or indirectly from data collected using specified assessments at specified timepoints
Withdrawal of Consent	Withdrawal of consent occurs only when a patient does not want to participate in the study any longer, and does not want any further visits or assessments, and does not want any further study related contact

1 Introduction

This Statistical Analysis Plan (SAP) provides detailed statistical methodology for the analysis of data from study LAG525X2101C that will be presented in the Clinical Study Report (CSR). The output shells (in-text and post-text) accompanying this document can be found in the TFL shells document. The specifications for derived variables and datasets can be found in the Programming Datasets Specifications (PDS) document. This version of the SAP is based on Protocol Amendment 10.

All changes to the planned analysis described in this document required before or after database lock will be made through an amendment or addendum, respectively. Note that obvious corrections will be made at the time of analysis to address minor formatting or spelling mistakes present in the TFL shells document without the need to amend.

The SAP, TFL shells and PDS documents may also serve as a reference for the creation of any outputs required outside of the CSR, e.g., MTD/RDE declaration, IB updates, abstracts, posters, presentations, manuscripts and management updates. Data used for these analyses will have a status aligned to the database lock guidance.

1.1 Study design

This study is a phase I/II, multi-center, open-label study which consists of 3 dose escalation parts (Arms A, B and C) with a staggered start, each followed by a Phase II part.

[figure not shown]
The first escalation is conducted with single-agent LAG525 in advanced solid tumors. The second dose escalation part is performed with the combination of LAG525 and PDR001 in advanced solid tumors. A separate Japanese dose escalation (Arm C) is performed in order to ensure that the safety and pharmacokinetic profiles of single-agent LAG525 are adequately characterized in Japanese patients at more than one LAG525 dose. Arms A and B are followed by a Phase II part after the determination of MTD/RP2D of single-agent LAG525 and combination of LAG525 and PDR001 respectively.

If the RP2D of single-agent LAG525 are the same in Arms A and C, patients enrolled in Japan could be recruited in Phase II single-agent part of the study. In addition, if the recommended dose of PDR001 for Japanese patients on the PDR001X1101 study are the same as that determined in study PDR001X2101, patients in Japan could also enter the combination parts of the study at whichever dose was being tested at that time.

Upon disease progression, patients assigned to LAG525 monotherapy during dose escalation may switch to LAG525 + PDR001 at a combination dose level that uses the patient's same LAG525 dose (or less) and has been determined safe and tolerable in previous dose escalation patients. If there is no combination dose level that includes the patient's LAG525 monotherapy dose, the patient may receive a lower dose level of LAG525 when switching to LAG525 in combination with PDR001;

The study design is summarized in [Figure 1-1](#).

Figure 1-1

Note: In the single agent LAG525 dose escalation (Arm A) at least 21 patients are required to define the RP2D; in the combination dose escalation (Arm B) at least 15 patients are required to define the RP2D and in the Japanese single agent LAG525 dose escalation (Arm C) at least 12 patients are required to define the RP2D.

The final clinical study report (CSR) will be based on all patients’ data from both phase I and phase II parts.

As antitumor activity was not observed with LAG525 single agent but was seen at several dose levels of LAG525 in combination with PDR001, it was decided that only the combination portion of Phase II would be enrolled.

1.2 Objectives and endpoints

Objective	Endpoint
Primary	
Phase I part To estimate the RP2D or MTD for:	The incidence of dose limiting toxicities (DLTs) during the first cycle of treatment with single agent LAG525. For the combination treatment of LAG525 and PDR001, the DLT window will be 2 cycles of the treatment.

 • Single agent LAG525 (including Japanese patients) 	

 • Combination of LAG525 and PDR001. 	

Phase II part To estimate the overall response rate per RECIST V1.1	Overall response rate per “Response Evaluation Criteria in Solid Tumors (RECIST) V 1.1”
--	---

- Single agent LAG525
- Combination of LAG525 and PDR001

[figure not shown]
Secondary

Phase I and Phase II parts: To characterize the safety and tolerability of single agent LAG525 given alone and in combination with PDR001	
● Safety incidence and severity if adverse events (AEs) and serious adverse events (SAEs) including changes in laboratory parameters, vital signs and ECGs ● Tolerability: Dose interruptions, reductions and dose intensity.
--	--

To characterize the pharmacokinetic profile of single agent LAG525 given alone and in combination with PDR001	
● Serum PK parameters (e.g. AUC, Cmax, Tmax, t_{1/2} half-life)
---	---

To assess emergence of anti-LAG525, and anti-PDR001 antibodies following one or more intravenous (i.v.) infusions of single agent LAG525 given alone or in combination with PDR001	
● Presence and/ or concentration of anti-LAG525 and anti-PDR001 antibodies
--	--

Phase II part: 
● To evaluate the preliminary antitumor activity of single agent LAG525 given alone or in combination with PDR001	
● ORR per immune related Response Criteria (irRC), PFS, DOR, DCR per RECIST V1.1 and per irRC
--	---

2 Statistical Methods

2.1 Data analysis general information

The statistical analysis of this study will be performed by Novartis personnel or a designated third party. A detailed description of the statistical analysis methods will be provided in Appendix 16.1.9 of the primary CSR. R version 2.13.2 (or later version), JAGS and WinBUGS version 1.4.3. will be used for Bayesian modeling. PK parameters will be calculated using non-compartmental methods available in *Phoenix* WinNonlin version 5.2. *SAS*® 9.3 or later (SAS Institute Inc., Cary, NC, USA) will be used in all other analyses.

The study data will be analyzed and reported (in a final CSR) based on all patients' data of the dose escalation and Phase II parts up to the time when all patients have potentially completed treatment or discontinued the study. The final CSR will include all outputs planned within TFL shells document.

Data from participating centers in this study protocol will be combined, so that an adequate number of patients will be available for analysis. No center effect will be assessed. The data will be summarized with respect to demographic and baseline characteristics, efficacy observations and measurements, safety observations and measurements, and all relevant pharmacokinetic (PK) [REDACTED] measurements using descriptive statistics (n, mean, standard deviation, median, minimum, and maximum) for quantitative data and contingency tables (frequencies and percentages) for qualitative data.

Both pre and post intra patient dose escalation data will be listed and summarized together under the one dose level/treatment group.

The following rules will be applied for reporting results unless stated otherwise:

- For the phase I part data will be analyzed by Arm, and cohorts treated with the same dose or dose combination (dose levels and schedules) will be pooled into a single treatment group by Arm. All summaries, listings, figures and analyses will be performed by treatment group and Arm. Arms to be analyzed are:
 - Arm A: Single agent LAG525
 - Arm B: Combination LAG525 + PDR001
 - Arm C: Single agent LAG525 dose escalation in Japanese patients
- For the phase II, all summaries, listings, figures for primary efficacy analysis and safety analyses will be presented by disease group and/or by dose group for one or more disease groups whenever applicable. Patients from Phase II will be classified according to the disease group to which they were assigned at baseline based on the disease type.
- The study treatment groups that were analyzed in the Phase II combination LAG525 + PDR001 cohorts were
 - Group 6: combo LAG525+PDR001, NSCLC (naïve to PD-1/PD-L1)
 - Group 7: combo LAG525+PDR001, Melanoma (naïve to PD-1/PD-L1)
 - Group 8: combo LAG525+PDR001, Renal cancer (naïve to PD-1/PD-L1)

- Group 9: combo LAG525+PDR001, NSCLC (pre-treated with PD-1/PD-L1)
- Group 10: combo LAG525+PDR001, Melanoma (pre-treated with PD-1/PD-L1)
- Group 12: combination LAG525+PDR001, Renal cancer (pre-treated with PD-1/PD-L1)
- Group 13: combo LAG525+PDR001, Mesothelioma (naïve to PD-1/PD-L1)
- Group 14: combo LAG525+PDR001, TNBC (naïve to PD-1/PD-L1)
- Group 15: combo LAG525+PDR001, Mesothelioma (pre-treated with PD-1/PD-L1)
- Group 16: combo LAG525+PDR001, TNBC (pre-treated with PD-1/PD-L1)

For phase I, all summaries, listings, figures for primary efficacy analysis and safety analyses will be presented by dosing regimen whenever applicable. Data from Arm A and Arm C will be pooled for safety and efficacy data.

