3. it is the dose recommended for patients, either per the model or by review of all clinical data by Novartis and Investigators in a dose-escalation teleconference, see [Section 6.2.3.1](#).

To better understand the safety, tolerability, PK [REDACTED] of single-agent LAG525 or combinations of LAG525 and PDR001, additional cohorts of patients may be enrolled at preceding dose levels, or to intermediate dose levels before or while proceeding with further dose escalation.

If a decision is made to escalate to a higher dose level but one or more additional patient(s) treated at the preceding dose level experiences a DLT during the DLT window, then the BLRM will be updated with this new information before any additional patients are enrolled at that higher dose level. Subjects ongoing will continue treatment at their assigned dose levels.

If the circumstance arises that a MTD is not reached in either single agent LAG525 escalation or that of the combination, then the RP2D of that arm will be determined from a synthesis of all data available, including safety and tolerability, pharmacokinetic [REDACTED] assessments and any preliminary antitumor activity observations.

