### **6.2.3.2 Intra-Patient dose escalation**

Intra-patient dose escalation is not permitted at any time within the first 4 cycles of treatment. After the 4th cycle is completed, individual patients may be considered for treatment at a dose of single agent LAG525 or in combination with PDR001, higher than the dose to which they were initially assigned. Only one of the study drugs will be escalated at any one time. Study drugs will be escalated as detailed in [Section 6.2.2](#). In order for a patient to be treated at a higher dose of either single agent LAG525 or in combination with PDR001, he or she must have tolerated the lower dose combination for at least 4 cycles of therapy (e.g., he or she must not have experienced at the lower dose level originally assigned a toxicity of CTCAE grade  $\geq 2$  considered related to study drug). Moreover, the new, higher dose combination with which the patient is to be treated must be a dose combination that has completed evaluation in a dose-escalation meeting and satisfies the EWOC criterion under the Bayesian model given all available data.

There is no limit to the number of times a patient may have his or her dose of LAG525 increased as a single agent or in combination with PDR001. Any further increases after the initial intra-patient dose escalation are subject to the same rules as for the initial intra-patient escalation. Consultation with Novartis must occur prior to any intra-patient dose escalation occurring. These changes must be recorded on the Dosage Administration Record CRF.

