2.2 Analysis sets

The number (%) of patients in each of the defined analysis set will be summarized using the Full Analysis Set (FAS).

Full Analysis Set

The FAS comprises all patients who received at least one full or partial dose of assigned single-agent LAG525, or at least one full or partial dose of assigned combination of study drugs. Patients will be analyzed according to the planned treatment. The FAS will be used for all listings of raw data. Unless otherwise specified, the FAS will be the default analysis set used for all analyses.

Safety Set

The Safety Set includes all patients from the FAS who have received at least one dose of LAG525 or PDR001. Patients will be classified according to treatment received, where treatment received is defined as:

1. The treatment assigned if it was received at least once, or
2. The first treatment received when starting therapy with study treatment if the assigned treatment was never received.

The safety set will be used for the safety summary of the study.

Per-Protocol Set

The Per Protocol Set (PPS) consists of a subset of FAS patients in the phase II part who meet the following criteria:

- Presence of at least one measurable lesion according to RECIST 1.1 as per Study Protocol Appendix 1
- At least 2 post-baseline tumor assessments (unless disease progression according to RECIST 1.1 is observed before that time)
- Have received the planned treatment

Patients will be classified according to planned treatment.

The PPS will be used in the phase II part of the study only and will define the patients used in the sensitivity analysis of the primary endpoint. If the PPS and the FAS are identical, then analyses described by the PPS below will not be performed.

Dose- Determining Analysis Set

Single agent LAG525 escalation cohort

The dose-determining analysis set (DDS) consists of all patients from the safety set in the dose escalation part who either meet the minimum exposure criterion and have sufficient safety evaluations, or have experienced a DLT during Cycle 1.

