PFS, along with DOR and time to response (TTR) for patients who experience a CR or PR at any time on study, will be listed by patient. Median PFS time and the proportion of patients who are progression-free at 3, 6, 9, and 12 months will be estimated for each group.

For patients who switched from single agent LAG525 to combination with PDR001, the efficacy information will be censored at the date of last adequate assessment before the switch. All efficacy assessments after the switch will be listed and flagged.

2.7.3 Waterfall plot for best overall response and best percentage change from baseline for all target lesions for each patient

The waterfall plot per RECIST 1.1 for all patients is the sum of the longest diameter of all target lesions for each patient by treatment. The FAS will be used to depict anti-tumor activity by treatment.

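### Phase I by-dose summaries pool data from before and after an intra-patient dose increase under the assigned dose, with no flag and no supportive summary cut at the increase

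*SAP*

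**What the plan says.** SAP section 2.1 sets the reporting rule: "Both pre and post intra patient dose escalation data will be listed and summarized together under the one dose level/treatment group". It does not say which dose level is meant, but SAP section 2.2 settles it. For the Full Analysis Set, "Patients will be analyzed according to the planned treatment". The Safety Set goes by treatment received, whose first branch is "The treatment assigned if it was received at least once, or" a fallback for patients who never received their assignment. Both lead to the dose first assigned.

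Protocol 6.2.3.2 governs the increases. "Intra-patient dose escalation is not permitted at any time within the first 4 cycles of treatment". After that, a patient may move up after tolerating the current dose for at least four cycles without related grade 2 or worse toxicity. The higher dose must have been through a dose-escalation meeting and must satisfy the overdose criterion, and the sponsor must be consulted. On repeat increases: "There is no limit to the number of times a patient may have his or her dose of LAG525 increased", each under the same rules.

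The SAP treats the other within-patient change differently. For patients who move from single-agent LAG525 to the combination, "the efficacy information will be censored at the date of last adequate assessment before the switch", with later efficacy assessments listed and flagged (SAP 2.7.2). SAP 2.8 also ends their on-treatment period 30 days after the last single-agent dose and flags later safety data.

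**The concern.** Phase I results are reported by treatment group, which the SAP glossary defines by dose and regimen. A reader takes a column headed with one dose to describe that dose. Under the SAP 2.1 rule the column can also hold events and responses that first appeared after the patient had moved to a higher dose.

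At stake is the by-dose description of later safety and of antitumour activity in the study report and in documents built from it. SAP section 1 says the plan may also serve as a reference for investigator brochure updates, publications and MTD/RDE declaration. Protocol 6.2.3 adds that, where no MTD is reached, the recommended dose draws on safety and tolerability, pharmacokinetic "assessments and any preliminary antitumor activity observations".

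**Working it through.** The plan gives no figure for this point, so there is nothing to reproduce. The check sets timing, counting rules and visibility side by side.

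**1. Which analyses can be touched.** Earliest increase = 4 × cycle length (Protocol 6.2.3.2). DLT window = 1 or 2 × cycle length (Protocol 6.2.4).

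| Schedule | Cycle (days) | DLT window, Arms A and C | DLT window, Arm B | Earliest increase |
|---|---|---|---|---|
| Q2W or Q4W | 28 | 28 | 56 | 4 × 28 = day 112 |
| Q3W | 21 | 21 | 42 | 4 × 21 = day 84 |

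The DLT window always closes before an increase is possible, so the dose-determining set, the BLRM and the MTD estimate are clean. Dose proportionality uses Cycles 1 and 3 (SAP 2.9), also before any increase. Phase II response is analysed by disease group, and the intra-patient rule sits in the dose-escalation guidelines, so it is not materially affected.

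**2. Which outputs run past the increase.**
- Adverse events and laboratory values: first dose to 30 days after last dose (SAP 2.8 and 2.8.2.3).
- Best overall response: treatment start to progression or new antineoplastic therapy (SAP 2.7.1), summarised by treatment group in Phase I (SAP 2.7.2). Disease control rate, PFS and duration of response follow the same assessments.

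Neither window is cut at a dose increase.

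**3. Direction, by counting.** SAP 2.8.1.2 counts each patient once per event category, at maximum grade. In a group of n patients, let a have the event before any increase and b have it only afterwards. The pooled incidence is (a + b)/n; cut at the increase it is a/n. Since b ≥ 0, pooling raises the figure or leaves it unchanged. The same count applies to ORR if responders are classed by when response was first documented.

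That comparison is between two ways of summarising the same patients. It does not give the bias against the true rate at the assigned dose. Escalated patients are selected for tolerating four cycles. Protocol 6.2.4 notes that some immune-related events have prolonged latency, and SAP 2.7.1 that response may be delayed. An event after an increase may therefore stem from the earlier dose.

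**4. Size.** The shift is b/n, and the documents give neither the number escalated nor b. For illustration only, take the prior mean DLT rates in Protocol Table 14-8 as stand-ins for late-toxicity rates (0.069 at 1 mg/kg, 0.11 at 3, 0.205 at 10). Assume a share f of a 1 mg/kg group is escalated and simply takes on the higher dose's rate. The reported rate is (1 − f) × 0.069 + f × p(high):

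| f (assumed) | Moved to 3 mg/kg | Moved to 10 mg/kg |
|---|---|---|
| 0 | 6.9% | 6.9% |
| 10% | 7.3% | 8.3% |
| 25% | 7.9% | 10.3% |
| 50% | 9.0% | 13.7% |

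This shows the mechanism. It ignores selection for tolerance and is not an estimate.

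**5. What a reader of the tables would see.** The dose-change tables count reductions and interruptions only (SAP 2.5.1.2). Planned cumulative dose is the sum of doses prescribed at each infusion (SAP 2.5.1.1), so relative dose intensity does not move when the prescribed dose rises. Dose intensity itself is neither summarised nor listed. Only the listing of doses shows the increase.

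**The case against.** Several points on the other side stand.

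- **The number escalated is unknown.** If nobody was escalated, the effect is nil.
- **Per-event shifts taken from Protocol Table 14-22 do not carry over.** A reader might note its groups of 3 to 12 patients and infer that one event moves a rate by 8 points (1/12) to 33 points (1/3). That table holds 43 DLT-evaluable Arm A patients (12 + 11 + 4 + 4 + 5 + 3 + 4) at a January 2016 cut-off. The Amendment 10 study status reports 134 single-agent and 121 combination patients in escalation, and SAP 2.1 pools Arms A and C for safety and efficacy. Those small denominators are not the ones in the planned tables.
- **A tenfold gap between label and dose is an extreme case.** Moving stepwise from 1 to 3 to 10 mg/kg needs two tolerated periods of four cycles: 8 × 28 = 224 days.
- **Misattributed responses matter mainly in Arm B.** SAP 1.1 states that no antitumour activity was seen with the single agent.
- **The switch comparison is partial.** Switchers add a second drug after progression, and Protocol 6.2.3.2.1 itself keeps their later responses out of ORR. Analysis by assigned dose is a legitimate pre-specified choice.
- **Replacing the main tables with ones censored at the increase would bring its own bias.** It removes follow-up selectively from patients who tolerated treatment and loses responses confirmed after the increase.

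It is also true that dose at onset can be rebuilt from the dose listing and study days. That takes patient-by-patient linkage, which by-dose tables exist to spare the reader. These points limit the size of the problem and the remedy. They do not supply the missing flag or supportive analysis.

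**Conclusion.** The point holds as a labelling and transparency gap in secondary Phase I reporting. By-dose summaries can attribute outcomes first seen at a higher dose to a lower one, with no flag and no sensitivity analysis. It rests on reading the one group as the initially assigned dose, which is the only reading consistent with SAP 2.2. The size cannot be computed.

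A reader might infer two stronger claims that the documents do not support. The first is that low doses will look more toxic and more active than they truly are. Pooling raises or leaves unchanged the incidence against a cut summary, but the direction against the true rate at the assigned dose is open. The second is that the rule distorted the choice of recommended dose. Protocol 8.5 has those decisions made at teleconferences where each patient's course, including later cycles, is discussed. The Amendment 9 study status also records 212 Phase II patients treated by June 2018, before the SAP amendments dated 2019 to 2021. What remains is interpretation by dose in the study report and its derivatives. This is a cheap improvement, not a threat to the primary analyses.

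**What to change.** Keep the assigned-dose summaries as the main tables, and amend the SAP 2.1 sentence so that:

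- (a) every adverse event, laboratory value and tumour assessment on or after the first dose above the assigned level is flagged in the listings, with the dose at onset or assessment;
- (b) Phase I adverse-event summaries are also given for the period before the first increase, with later events in a separate table by dose at onset;
- (c) a supportive Phase I best-response and ORR summary counts only responses first documented before the first increase, allows confirmation after it, and footnotes responders first documented later.

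Reporting the number of escalated patients per assigned dose alongside these would show whether the issue matters. Censoring PFS or duration of response at the increase is not proposed, for the reason given above.

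Dose changes and dates are already on the Dosage Administration Record, so no new data and no change to patient management are needed. The cost is one period flag, a few extra tables, and shorter follow-up in the supportive pre-increase summaries.
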